**Impact of Retro-molar pad carving on complete denture wearers satisfaction and quality of life: a cross-over, double-blind clinical trial.**

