### **Statistical analysis:**

The SPSS computer software (IBM SPSS Statistics v21.0; IBM Corp., USA) was utilized for the statistical analysis of the collected data in this study. The significance of the conducted statistical results was considered at two tailed  $\alpha$  of .05. Normal distribution of the data was tested utilizing the Shapiro-Wilk test and the skewness test considering skewness z-score threshold values range from -3.29 to +3.29. All the continuous variables were not normally distributed, except for age and OHIP scores before treatment. Descriptive statistics for normally distributed continuous variables (age and OHIP scores before treatment) included the mean, standard error, standard deviation, median, maximum value, minimum value, and confidence intervals. Meanwhile, descriptive statistics for the non-normally distributed continuous variables included the mean, standard deviation, median, interquartile range, minimum value, and maximum value. Categorical variables in this study (presence of redness, erosion, keratosis, ulceration, and denture fissuratum) were presented as frequencies and percentages.

The Wilcoxon Signed Ranks test was used to test paired differences in satisfaction ratings, dentist's evaluations, and OHIP-EDENT scores after using carved and non-carved lower dentures. The Mann Whitney U test was utilized to identify differences in satisfaction ratings, dentist's evaluations, and OHIP-EDENT scores between genders. Spearman's Rho rank correlations were used to identify the correlations between satisfaction ratings, dentist's evaluations, and OHIP-EDENT scores. Associations between identification of lesions following denture use (presence of redness, erosion, keratosis, ulceration, and denture fissuratum) and having the retromolar pad area of the lower denture carved or not were tested via Fisher's Exact test.

The multiple linear regression analysis was used to identify the contribution of having the retromolar pad area carved or not, satisfaction ratings, and dentist evaluation towards the prediction of OHIP-EDENT scores considering the confounding effects of gender and age.

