## Results

The data was collected from a total of 49 participants (23 females and 27 males), and was then processed and analyzed. Participants age ranged from 40 to 78 years old (mean age= 62.8 years old, SD= 8.01, SE= 1.145, median= 63.0, 95% CI= 60.51 – 65.12).

Table 1 demonstrates the descriptive statistics for continuous variables in this study including dentist evaluations of dentures, patients' satisfaction with dentures, and OHIP-EDENT scores among the participants of this study. Paired comparisons of carved and non-carved lower dentures showed that patient satisfaction with retention at function ( $P= .002$ ) and comfort during the use of carved lower dentures ( $P= .026$ ) were significantly higher than non-carved lower dentures (Table 1). Furthermore, the patients demonstrated a tendency to be more satisfied with denture retention at rest as well as during eating when used carved lower dentures in comparison to non-carved ones. This difference was not significant but was close to be significant ( $P= .052$ ,

Table 1). In addition, carved lower dentures were associated with lower OHIP scores (better impacts on oral health) than the non-carved lower dentures; however, the difference was not significant ( $P= .055$ , Table 1). Nevertheless, this tendency was confirmed by the Mann Whitney U test as a significant difference was found in the OHIP scores between carved and non-carved lower dentures ( $MWU= 887.0$ ,  $Z= -2.241$ ,  $P= .025$ ). The carved lower dentures were associated with lower OHIP scores indicating better impacts on oral health than the non-carved dentures.

Table 2 presents the distribution (frequencies and percentages) of redness, erosion, keratosis, ulceration, and denture fissuratum following the use of the tested complete denture designs during this study. Redness was the most observed mucosal change, 18.4% with non-carved dentures and 12.2% with carved dentures. No significant differences in mucosal changes were observed between carved and non-carved lower dentures ( $P> .05$ , Table 2).

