Smile and appearance of upper and carved lower dentures	9.65	0.694	10.0	7.0	10.0	0.5		
Retention during speaking with upper and non carved lower dentures	9.14	1.414	10.0	3.0	10.0	1.0	-.662	.508
Retention during speaking with upper and carved lower dentures	9.10	2.400	10.0	0.0	20.0	2.0		
OHIP scores								
OHIP scores before dentures	22.59	10.82	20.0	4.0	48.0	17.0		
OHIP scores after using NCLD	11.12	7.793	9.0	2.0	39.0	8.0	-1.916	.055
OHIP scores after using CLD	8.45	6.433	6.0	0.0	31.0	7.5		

NCLD= Non-carved lower denture, CLD= Carved lower denture, OHIP= Oral Health Impact Profile – 14, SD= Standard deviation, Med= Median, Min= Minimum value, Max= Maximum value, IQR= Interquartile range, Z= Z statistic using Wilcoxon signed ranks test, P= Two-tailed probability value.

**Table 2.** Distribution of redness, erosion, keratosis, ulceration, and denture fissuratum following the use of the tested complete denture designs in this study (N= 50).

Variables	Non-carved lower denture				Carved lower denture				Comparison between carved and non-carved dentures	
	No		Yes		No		Yes			
	Fre	%	Fre	%	Fre	%	Fre	%	Z	P
Redness	40	81.6	9	18.4	43	87.8	6	12.2	-0.837	.402
Keratosis	49	100.0	0	0	49	100.0	0	0	0	1.00
Erosion	48	98.0	1	2.0	47	95.9	2	4.1	-0.583	.560
Ulceration	48	98.0	1	2.0	49	100.0	0	0	-1.000	.317
Denture Fissuratum	49	100.0	0	0	49	100.0	0	0	0	1.00

Fre= Frequency, % = Percentage. Z= Z statistic using Wilcoxon signed ranks test, P= Two-tailed probability value.

Table 3. Paired comparisons of dentist and patient denture ratings between upper complete dentures and each tested design of lower dentures in this study (N= 50).

Compared pairs	Z	P
Dentist evaluation of dentures		
Retention of NCLD versus upper denture	-2.887	.004
Retention of CLD versus upper denture	-1.506	.132
Stability of NCLD versus upper denture	-1.343	.179
Stability of CLD versus upper denture	-.854	.393
Support of NCLD versus upper denture	-2.558	.011
Support of CLD versus upper denture	-1.165	.244
Esthetic of NCLD versus upper denture	-0.019	.985
Esthetic of CLD versus upper denture	-0.153	.879
Patient satisfaction with dentures		
Pain due to NCLD versus upper denture	-2.653	.008
Pain due to CLD versus upper denture	-1.178	.239
Retention at rest of NCLD versus upper denture	-2.104	.035
Retention at rest of CLD versus upper denture	-0.285	.775
Retention at function of NCLD versus upper denture	-4.149	.000
Retention at function of CLD versus upper denture	-1.831	.067

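### A non-significant paired OHIP result (P = .055) is declared confirmed by an unpaired Mann-Whitney test (P = .025) on the same cross-over scores

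*SAP*

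**What the plan says.** The title describes "a cross-over, double-blind clinical trial", so both OHIP scores come from the same person.

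The SAP's Statistical analysis section allots the tests clearly. For the comparison of the two denture designs: "Wilcoxon Signed Ranks test was used to test paired differences in satisfaction ratings, dentist's evaluations, and OHIP-EDENT scores after using carved and non-carved" designs. The unpaired test has a different job: "The Mann Whitney U test was utilized to identify differences in satisfaction ratings, dentist's evaluations, and OHIP-EDENT scores between genders". On the threshold: "The significance of the conducted statistical results was considered at two tailed" alpha of .05.

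The Results first give the planned comparison. OHIP scores were lower with carved dentures "than the non-carved lower dentures; however, the difference was not significant" (P = .055; Table 1 gives Z = -1.916). The next sentence reverses the message: "this tendency was confirmed by the Mann Whitney U test as a significant difference was found in the OHIP scores between carved and non-carved" designs, with U = 887.0, Z = -2.241 and P = .025. The paragraph ends by stating the advantage of the carved denture without qualification.

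For mucosal lesions, which are also recorded under both dentures in each person, the methods say that associations with "having the retromolar pad area of the lower denture carved or not were tested via Fisher's Exact test". The footnote to Table 2 says otherwise: "Fre= Frequency, % = Percentage. Z= Z statistic using Wilcoxon signed ranks test".

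**The concern.** The Mann-Whitney test assumes two independent groups. Here the two sets of scores come from the same people, so the assumption fails by design. The test is also applied to the very scores that the signed-rank test has already used, so agreement in direction is guaranteed or nearly so and adds no evidence.

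The two P values lie on opposite sides of .05, and the text adopts the favourable one. No other near-miss in Table 1 gets this treatment: patient-rated retention at rest and retention during eating (both P = .052) are left as not significant. At stake is whether the trial may say that carving gives a statistically significant gain in oral-health-related quality of life, an outcome named in its title.

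**Working it through.** **Inputs.** Results: U = 887.0, Z = -2.241, P = .025, and 49 participants analysed. Table 1: OHIP mean 11.12 (SD 7.793) non-carved and 8.45 (SD 6.433) carved; paired Z = -1.916, P = .055. Table 2: lesion counts out of 49 per denture.

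**1. Printed P values.** With P = 2Φ(-|Z|), Z = -1.916 gives P = .0554 and Z = -2.241 gives P = .0250. Both agree with the SAP.

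**2. What the Mann-Whitney test compared.** Before correction for ties, Z = (U - n₁n₂/2) / √(n₁n₂(n₁+n₂+1)/12).

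- 49 against 49: mean 49 × 49/2 = 1200.5; SD √(49 × 49 × 99/12) = 140.74; Z = (887 - 1200.5)/140.74 = -2.227, P = .026. The printed -2.241 implies an SD of 313.5/2.241 = 139.89, a variance ratio of 0.988. That is a small tie correction, as expected with integer scores.
- 49 against 50: Z = -2.366, P = .018.
- 50 against 50: Z = -2.502, P = .012.
- A gender split (27 and 23): U cannot exceed 27 × 23 = 621, so 887 is impossible.

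A tie correction can only increase |Z|, so neither of the two larger group sizes can give -2.241. The test took 98 scores from 49 people as two independent groups of 49.

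**3. The result under the stated method.** Keeping only the test named in the methods leaves Z = -1.916, P = .0554, with an observed mean difference of 11.12 - 8.45 = 2.67 points.

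**4. Precision.** The SAP does not give the within-person correlation r between the two OHIP scores, so an interval needs an assumption. SD of the difference = √(7.793² + 6.433² - 2r × 7.793 × 6.433); the 95% CI is 2.67 ± 2.011 × SD/√49.

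- r = 0: SD 10.105, CI -0.2 to 5.6.
- r = 0.2: SD 9.059, CI 0.07 to 5.3.

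These are t-based illustrations on skewed scores and do not replace an interval computed from the actual pairs.

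**5. Lesions (minor).** For binary pairs the signed-rank statistic is |b - c|/√(b + c), where b and c count people with the lesion under one denture only. The number with the lesion under both dentures is not given, so every possible overlap was tried, assuming 49 complete pairs.

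| Lesion (non-carved, carved) | Printed \|Z\|, P | Unpaired, tie-corrected \|Z\| | Fisher P | Possible signed-rank \|Z\| | Exact McNemar P |
|---|---|---|---|---|---|
| Redness (9, 6) | 0.837, .402 | 0.8374 | .576 | 0.775, 0.832, 0.905, 1.000, 1.134, 1.342, 1.732 | .25 to .61 |
| Erosion (1, 2) | 0.583, .560 | 0.5834 | 1.0 | 0.577, 1.000 | 1.0 |
| Ulceration (1, 0) | 1.000, .317 | 1.000 | 1.0 | 1.000 | 1.0 |

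Fisher's test reproduces none of these rows. The redness and erosion values fit only an unpaired Mann-Whitney test. Ulceration fits both rank tests, and the rows with no events cannot distinguish them.

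**The case against.** The strongest defence is that nothing is concealed. The planned paired result comes first, is called not significant, and appears again in Table 1; the Mann-Whitney test is named with its U, Z and P. The later Results text does not list carving among the significant predictors of OHIP, and Table 6 gives B = -1.324, P = .282 for carving. This limits how far a careful reader is misled. It does not rescue the sentence, which states that a significant difference was found. Table 6 is context only: its model adjusts for pain and satisfaction measured after denture use, and its confidence limits fit 98 rows less 17 parameters (81 degrees of freedom), so it ignores the pairing too.

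A second defence is that ignoring positive within-person correlation usually makes the unpaired test conservative. That is correct. In an illustrative simulation with no true difference (3,000 trials of 49 pairs, skewed rounded scores, correlation assumed), Mann-Whitney rejected in 8.9%, 5.0%, 2.7% and 0.8% of trials at r = -0.3, 0, 0.2 and 0.5. Either test rejected in 9.5%, 6.8%, 5.5% and 4.8%. So material inflation of the type I error cannot be shown from the document, and this point does not rely on it. What stands is that the test does not suit the design, was not the stated method, and is no independent confirmation.

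It is also fair to say that P = .055 is not evidence of no effect. The intervals above, which lie close to zero at one end and reach more than 5 points at the other, support that, and are why the estimate should be reported.

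**Conclusion.** The concern holds. The claim of a statistically significant OHIP difference rests only on an unpaired test applied to paired scores. Under the test that the SAP itself names, the result is P = .055, not significant at two-sided .05. The direction and observed size of the difference, 2.67 points in favour of the carved denture, are not in dispute; only the inference changes. The finding that 98 scores were treated as independent follows from the printed U and Z and needs no assumption about correlation. The discrepancy between 49 and 50 participants elsewhere in the SAP is a separate matter and does not affect this. Because the sentence changes the stated inference on a title outcome, it must be corrected.

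The lesion part is a fault of method and labelling. Its conclusion of no significant difference stands under exact McNemar tests at any possible overlap.

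**What to change.** - Delete the Mann-Whitney comparison of carved and non-carved OHIP scores and the confirmation wording, and qualify the closing sentence of that paragraph.
- Report the signed-rank result as not significant at two-sided .05 (P = .055), with the paired difference and its 95% confidence interval computed from the individual pairs, for example a Hodges-Lehmann estimate to match the signed-rank test.
- For lesions, name McNemar's exact test in the methods, rerun it for redness, erosion and ulceration, and correct Table 2 and its footnote.

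The cost is small: one results passage reworded, one interval and three tests run on data already held, and the methods text and one footnote corrected. The OHIP statement becomes less favourable to carving; the lesion conclusion stays as it is.

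### Mucosal lesions are reported only as P values: four of the five comparisons could not have reached .05 with the events seen, no interval is given, and the test is inconsistently described (minor)

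*SAP*

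**What the plan says.** The Statistical analysis section presents the lesions as frequencies and percentages. It says that associations between the lesions and "having the retromolar pad area of the lower denture carved or not were tested via Fisher's Exact test". The criterion is general: "The significance of the conducted statistical results was considered at two tailed" .05. No paired difference, confidence interval or margin is planned for lesions.

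The Results give the redness percentages (18.4% non-carved, 12.2% carved) and then one sentence covering all five lesions: "No significant differences in mucosal changes were observed between carved and non-carved lower dentures", with P > .05.

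Table 2 prints counts, percentages, Z and P. Its footnote reads "Fre= Frequency, % = Percentage. Z= Z statistic using Wilcoxon signed ranks test", so it names a different test from the methods. The keratosis row is "Keratosis 49 100.0 0 0 49 100.0 0 0 0 1.00" and the erosion row is "Erosion 48 98.0 1 2.0 47 95.9 2 4.1 -0.583 .560". Denture fissuratum has the same entries as keratosis. The table title gives N = 50, but each row sums to 49 per denture, in line with the Results: "The data was collected from a total of 49 participants".

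**The concern.** These lesions are the only tissue-harm outcome in the document. A P value above .05 says something about harm only if a P below .05 was attainable, or if an interval shows which differences the data rule out. Neither holds for the rarer lesions. One pooled sentence puts redness, with 15 events, beside lesions with three, one or no events, as though all five had been compared equally well.

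The test itself is also unclear. Each participant wore both dentures, so the comparison is paired. Fisher's exact test treats the two dentures as independent groups, Wilcoxon signed ranks does not, and the document names one in the methods and the other under the table. A reader who wants to rebuild the comparison does not know which was run, and the discordant pairs needed to redo it are not given.

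**Working it through.** **Inputs (Table 2).** n = 49 per denture. Events, non-carved v carved: redness 9 v 6; erosion 1 v 2; ulceration 1 v 0; keratosis 0 v 0; fissuratum 0 v 0. Two-sided .05 comes from the Statistical analysis section. The paired cross-tabulation is not given, so paired results are shown over every pairing that fits the margins.

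**Step 1: reproduce the printed Z and P.** For binary data, the unpaired Mann-Whitney normal approximation is z = (difference in proportions) / √[p̄(1 − p̄) · 2/49] × √(97/98), where p̄ is the pooled proportion.

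- Redness: p̄ = 15/98 = .1531; z = −.0612 / .0727 × .9949 = −0.837, P = .402. Printed: −0.837, .402.
- Erosion: p̄ = 3/98 = .0306; |z| = .0204 / .0348 × .9949 = 0.583, P = .560. Printed: −0.583, .560 (the sign depends on coding).
- Ulceration: |z| = 1.000, P = .317. Printed: −1.000, .317.

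Wilcoxon signed ranks on binary pairs gives |z| = |b − c| / √(b + c), where b and c are the discordant counts.

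- Redness: |b − c| = 3 and b + c can be 3, 5, 7, 9, 11, 13 or 15. This gives |z| = 1.732, 1.342, 1.134, 1.000, .905, .832 or .775, never .837.
- Erosion: |b − c| = 1 and b + c is 1 or 3. This gives 1.000 or .577, never .583.

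Fisher's exact test gives P = .576 (redness), 1.00 (erosion) and 1.00 (ulceration), not .402, .560 and .317. So the redness and erosion values match the unpaired Mann-Whitney test and neither of the named tests.

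**Step 2: smallest attainable P.** Keep each lesion's total number of events and put them all on one denture.

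| Lesion | Events | Mann-Whitney | Wilcoxon | Fisher | Exact McNemar |
|---|---|---|---|---|---|
| Keratosis, fissuratum | 0 | 1.00 | 1.00 | 1.00 | 1.00 |
| Ulceration | 1 | .317 | .317 | 1.00 | 1.00 |
| Erosion | 3 | .080 | .083 | .242 | .250 |
| Redness | 15 | <.001 | <.001 | <.001 | <.001 |

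The 1.00 in the zero-event row is a convention for the paired tests, which have no discordant pairs to work on. Reaching .05 takes at least four events, all on one denture, with the asymptotic tests (.042 and .046), and six with the exact tests (.027 and .031).

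**Step 3: what the data exclude.** The Bonett-Price paired interval adds one to each discordant count: p₁ = (b + 1)/51 for non-carved only, p₂ = (c + 1)/51 for carved only, D = p₂ − p₁, SE = √[(p₁ + p₂ − D²)/51], limits D ± 1.96·SE. D is slightly shrunk from the raw difference.

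- Redness, raw difference (6 − 9)/49 = −6.1 points. No participant affected with both dentures (b = 9, c = 6): D = −5.9, SE = 8.04, upper limit +9.9. All six carved cases also affected with the non-carved denture (b = 3, c = 0): SE = 4.31, upper limit +2.6.
- Erosion, raw difference +2.0 points. b = 1, c = 2: upper limit +10.5. b = 0, c = 1: upper limit +8.6.
- Ulceration, raw difference −2.0 points. b = 1, c = 0: upper limit +4.7.
- Keratosis and fissuratum, b = c = 0: limits ±5.4 points.

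For a single 0/49 rate, the two-sided exact 95% upper limit is 1 − .025^(1/49) = 7.25%, or 7.3%.

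**The case against.** A reader might infer that the document claims carving leaves lesion rates unchanged or is safe for the mucosa. It does not. The Results sentence reports non-significance, which is true, and nothing visible speaks of safety, tolerability or equivalence. Every count is printed, so an attentive reader can see how rare four of the lesions are. This defence stands and keeps the point minor. It does not supply the missing interval, and the pooled sentence does not say that four of its five components were uninformative.

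The P = 1.00 entries are not false in themselves: Fisher's exact test on 0/49 v 0/49 returns 1.00. They merely tell the reader nothing, and the footnote attributes them to a paired test for which there were no non-zero differences to rank.

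It is also tempting to say that the plan guaranteed P > .05 for these lesions. That goes too far. The limit in Step 2 is conditional on the event totals, known only afterwards; had carving produced many lesions, the totals would have been testable. Nor can a several-fold rise be asserted: the observed baselines are zero or one event, so a ratio is not usefully estimable, and the limits here are for differences. For redness, a doubling from 18.4% would be an increase of 18.4 points, which the paired interval excludes under every possible pairing.

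**Conclusion.** The point holds as a minor reporting and analysis correction. With the observed totals, four of the five lesion comparisons could not reach .05 under any of the four tests examined, so the pooled statement is informative only for redness. Depending on the pairing, the data exclude an increase in redness beyond +2.6 to +9.9 points. For the other lesions, increases of about 5 to 10 points are not excluded. Separately, the methods and the table footnote name different tests, and the printed redness and erosion values match a third, unpaired one.

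These results assume 49 complete pairs, as the Table 2 rows imply despite the N = 50 in its title. The ranges reflect the unreported cross-tabulation and would become single values once the discordant pairs are known. The match to the Mann-Whitney test is inferred from the printed figures, since the document does not say that this test was used for lesions.

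**What to change.** - **Statistical analysis section and Table 2:** replace the test wording with one paired analysis. Give the discordant-pair counts, the paired risk difference (carved minus non-carved) with a 95% interval such as Bonett-Price, and an exact McNemar P where discordant pairs exist. Make the footnote agree, and correct N to the number analysed.
- **Keratosis and fissuratum rows:** in place of Z and P, print: no events, 0/49, upper 95% limit 7.3%.
- **Results text:** report redness as 12.2% v 18.4% with its paired interval from the data. State that the other lesions were too few to compare and that increases of about 5 to 10 percentage points are not excluded.
- **Any combined row:** if a row for any mucosal lesion is added, label it post hoc. Do not add a pass/fail rule on the upper limit, because no margin was set in advance.

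The cost is a short re-run on data already held and a few lines of text. The downside is a less reassuring statement on the rare lesions.

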Table 5 presents correlations between age, patient satisfaction, and OHIP scores. The results show that older patients were more comfortable with upper dentures than younger patients (Spearman Rho= 0.309,  $P= .031$ , Table 5). Also, higher pain scores were associated with higher OHIP scores (i.e. worse impacts) after using carved ( $P= .001$ ) and non-carved ( $P< .001$ ) lower dentures (Table 5). In addition, lower OHIP scores (i.e. better impacts) were associated with higher satisfaction with retention at rest, retention at function, denture comfort, general satisfaction with dentures, retention during eating, and retention during speaking after using carved or non-carved lower dentures ( $P< .05$ , Table 5). Besides, correlations between age and dentist rating of dentures showed that older participants were found to have better dentist ratings of retention (Sperman Rho= 0.402,  $P= .004$ ) and higher stability (Spearman Rho= 0.402,  $P= .003$ ) of upper dentures than younger participants.

A multiple linear regression analysis was used to identify the contribution of having the retromolar pad area carved or not, satisfaction ratings, and dentist evaluation of dentures towards the prediction of OHIP scores considering the confounding effects of gender and age (Table 6). Being a female, having lower dentist ratings of denture esthetics, and having more pain due to lower dentures were associated with higher scores of OHIP indicating worse oral health impacts

of the prosthesis ( $P < .05$ , Table 6). Being a female was associated with an increase of OHIP scores by 4 units ( $P = .007$ ). Also, for each decreased unit of dentist ratings of denture esthetics, the OHIP scores were increased by 2 units ( $P = .018$ ). Furthermore, for each increased unit of pain levels due to lower dentures, the OHIP scores were increased by 0.7 units ( $P = .020$ ) (Table 6).

Further multiple linear regression analyses were conducted to identify the contribution of having the retromolar pad area carved or not and dentist evaluation of dentures towards the prediction of patient satisfaction with different denture aspects considering the confounding effects of gender and age (Table 7). The results showed that carved lower dentures were associated with 1.144 times higher satisfaction with lower denture retention during function ( $P = .040$ , Table 7). **[name] please note that Being carved or not was significant predictor for retention of the denture during function.**

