General satisfaction with upper and carved lower dentures	Rho	.058	-.316	-.491
	P	.695	.027	<.001
Retention during eating with upper and non carved lower dentures	Rho	.260	-.582	-.032
	P	.072	<.001	.828
Retention during eating with upper and carved lower dentures	Rho	-.069	-.320	-.459
	P	.639	.025	.001
Smile and appearance of upper and	Rho	-.102	-.290	-.196

non carved lower dentures	P	.484	.043	.177
Smile and appearance of upper and carved lower dentures	Rho	.181	-.359	-.207
	P	.213	.011	.153
Retention during speaking with upper and non carved lower dentures	Rho	.066	-.435	-.145
	P	.655	.002	.321
Retention during speaking with upper and carved lower dentures	Rho	-.016	-.276	-.505
	P	.911	.055	<.001
OHIP score before treatment	Rho	-.104	.253	-.052
	P	.479	.079	.722

NCLD= Non-carved lower denture, CLD= Carved lower denture, OHIP= Oral Health Impact Profile – 14, Rho= Spearman correlation coefficient, P= Two tailed probability value.

**Table 6.** Linear regression analyses to predict OHIP scores after treatment utilizing the demographic variables, having the lower denture carved or not, dentist ratings of lower dentures, and patient satisfaction with dentures among the study sample (n= 50).

Dependent variable	Predictors*	Unst Co		St Co	t	P	95% CI for B	
		B	SE	Beta			Lower Bound	Upper Bound
OHIP scores after treatment R  = .468 DW = 1.837	Constant	63.274	13.648	---	4.636	<.001	36.118	90.430
	Gender	4.063	1.465	.281	2.774	.007	1.149	6.977
	Age	-.132	.080	-.146	-1.645	.104	-.292	.028
	Carved denture or not	-1.324	1.222	-.092	-1.084	.282	-3.755	1.107
	Dentist rated lower denture retention	.314	.507	.084	.619	.538	-.695	1.323
	Dentist rated lower denture stability	-.704	.793	-.151	-.888	.377	-2.282	.873
	Dentist rated lower denture support	.477	.833	.069	.572	.569	-1.182	2.135
	Dentist rated lower denture esthetics	-2.070	.860	-.245	-2.408	.018	-3.780	-.359
	Perceived pain due to lower denture	.711	.299	.253	2.374	.020	.115	1.306
	Patient satisfaction with lower denture retention at rest	-.213	.473	-.064	-.451	.653	-1.154	.727
	Patient satisfaction with lower denture retention at function	-.281	.400	-.115	-.704	.484	-1.077	.514
	Patient satisfaction with lower denture Comfort	.090	.522	.033	.173	.863	-.948	1.128
	Patient satisfaction with easiness of lower denture insertion	-.359	.473	-.068	-.758	.450	-1.300	.583
	Patient general satisfaction with upper and lower dentures	-.244	.518	-.066	-.471	.639	-1.275	.787

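### The unqualified OHIP benefit rests on an unplanned, unpaired test; the planned test gave P = .055, and the text omits the planned regression's carving term and the dentist comparisons

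*SAP*

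**What the plan says.** **Plan (SAP, Statistical analysis).** The level is two-tailed .05. For carved against non-carved dentures, "The Wilcoxon Signed Ranks test was used to test paired differences in satisfaction ratings, dentist's evaluations, and OHIP-EDENT scores". The Mann-Whitney U test is assigned to differences between genders. For OHIP-EDENT, "The multiple linear regression analysis was used to identify the contribution of having the retromolar pad area carved or not", alongside satisfaction and dentist ratings, with gender and age as confounders. No regression on satisfaction scores is described there.

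**Results on OHIP.** OHIP was lower with carving; "however, the difference was not significant" (P = .055). The text then says that a Mann-Whitney test bears out the tendency (U = 887.0, Z = −2.241, P = .025). It closes the paragraph by associating carved dentures with lower OHIP scores, with no qualifier.

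**Results on the regressions.** The paragraph on Table 6 repeats that the aim is to identify the contribution of carving, then reports that "Being a female, having lower dentist ratings of denture esthetics, and having more pain due to lower dentures were associated with higher scores". The row "Carved denture or not" is not mentioned. From the further models in Table 7, the text gives the carving term for retention at function only.

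**Results on the paired tests.** The text begins "Paired comparisons of carved and non-carved lower dentures showed that patient satisfaction with retention at function" and comfort were significantly higher with carving. It continues with retention at rest, retention during eating and OHIP. The dentist comparisons of carved with non-carved dentures appear only in Table 1. The text does compare each lower design with the upper denture on dentist ratings (Table 3).

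**The concern.** Quality of life is in the trial's title, so the OHIP sentence is one that readers will carry away. A crossover gives each participant a score with each denture, and the plan rightly chose a paired test. That test missed .05. The statement that follows it in the text relies on a test that ignores the pairing and was not planned for this comparison.

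The carving term from the planned regression would have tempered the statement, but it is absent from the prose. The one Table 7 carving term below .05 is present.

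The dentist ratings raise a related issue. The text sets significant differences between upper and non-carved dentures against non-significant differences between upper and carved dentures. A reader may take that contrast as evidence that dentists rated carving better. The direct comparisons that answer the question are not stated.

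**Working it through.** **1. Planned paired tests (Table 1).** Two-sided P = 2 × [1 − Φ(|Z|)]. All 13 printed P values reproduce from their Z values. Those that matter here:

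| Comparison, non-carved v carved | Means | Z | P printed | P recomputed |
|---|---|---|---|---|
| OHIP | 11.12 v 8.45 | −1.916 | .055 | .055 |
| Dentist: retention | 8.02 v 8.34 | −1.357 | .175 | .175 |
| Dentist: stability | 8.36 v 8.63 | −1.906 | .057 | .057 |
| Dentist: support | 8.78 v 9.05 | −1.053 | .292 | .292 |
| Dentist: esthetics | 8.87 v 8.90 | −.223 | .824 | .824 |

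**2. The Mann-Whitney test.** Table 2 counts sum to 49 per denture (for example 40 + 9), so take 49 scores in each group. As independent groups:
- mean of U = 49 × 49 / 2 = 1200.5
- SD of U = √(49 × 49 × 99 / 12) = 140.74
- Z = (887 − 1200.5) / 140.74 = −2.23 without tie correction

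The printed Z is −2.241; a tie correction makes Z slightly larger in size. The test therefore compared 49 with 49 scores as if they came from different people. Z = −2.241 gives P = .025, as printed.

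**3. Carving term in the OHIP regression (Table 6).** The model has 16 predictors. With 49 × 2 = 98 rows, residual df = 98 − 17 = 81.
- t = −1.324 / 1.222 = −1.083 (printed −1.084)
- P = .282, as printed
- 95% CI = −1.324 ± 1.9897 × 1.222 = −3.755 to 1.107, as printed

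With 100 rows (df 83) the P and interval are the same to three decimals.

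**4. Carving terms in Table 7.** There are eight models, each with 8 predictors (df = 98 − 9 = 89). Printed P values are: retention at rest .394, retention at function .040, comfort .353, insertion .796, general satisfaction .388, eating .265, smile .930, speaking .464. Recomputed values agree within .002. One of eight is below .05. The other seven run from .265 to .930.

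**5. What the text covers.**
- Table 1 prints 13 carved v non-carved tests. Five are in the text: two significant, and three stated as not significant (retention at rest, eating, OHIP).
- Eight are not in the text: the four dentist ratings, pain (.057), insertion (.943), smile (.777) and speaking (.508).
- Table 2 prints five more comparisons, on mucosal changes (P = .317 to 1.00). One sentence reports them all as not significant.
- In total, 10 of 18 printed comparisons are covered.
- In Table 6 the text names the three predictors with P < .05 and omits the other 13, carving among them.

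**The case against.** A reader might infer that the text names carving only where the result is favourable. The document does not support that. The Results call OHIP, retention at rest and retention during eating non-significant, report no significant mucosal differences, and report more pain in females than in males with carved dentures. The omissions track the P value and not the direction: pain (2.08 v 1.20) and dentist stability (8.36 v 8.63), both P = .057 and both leaning towards carving, are also left out. In Table 6 carving is treated like every other predictor above .05. All the omitted figures are in tables that the text cites. The document has no conclusion section, and the retention finding is already worded as patient satisfaction. All of this stands.

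It can also be objected that P = .282 is a poor witness. The Table 6 model adjusts for pain, satisfaction and dentist ratings obtained with the dentures, which carving may itself change. The term therefore does not estimate the total effect of carving on OHIP and must not be read as showing none. This stands as a caveat on how to report the term. It does not excuse silence on the quantity that the plan says the model was there to identify.

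The objection does not reach the OHIP sentence. Stating P = .055 and then overriding it with an unpaired test leaves the reader with a claim that the planned paired test does not support at the plan's own level.

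**Conclusion.** The point holds in this form. The closing OHIP statement is wrong as written: the planned paired test gave P = .055 against a two-tailed .05, and the P = .025 that replaces it comes from an unplanned test that treats paired scores as independent. The text also omits the carving term of the planned OHIP regression (P = .282), seven of the eight carving terms in the further models of Table 7, and all four planned dentist comparisons.

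Three stronger readings are not supported. The document does not show concealment. It does not show that carving has no effect on OHIP: the observed mean is 11.12 − 8.45 = 2.67 points lower, and the adjusted interval runs from −3.755 to 1.107. Nor does it show that dentists saw no difference: the four comparisons are not significant, and all four means lean slightly towards carving (by 0.03 to 0.32 points). The nine regression carving terms should not be pooled into one count, because one model was planned and eight were further analyses.

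The recomputations assume 49 participants with two scores each.

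**What to change.** 1. **OHIP paragraph of the Results.** Remove the Mann-Whitney result and the sentence that rests on it. State that OHIP scores were lower with carving and that the planned signed-rank test was not significant at .05 (Z = −1.916, P = .055).
2. **Regression paragraphs.** Report the Table 6 carving term (B −1.324, 95% CI −3.755 to 1.107, P = .282). Add that the model adjusts for post-treatment pain, satisfaction and dentist ratings and so does not estimate the total effect of carving. For Table 7, say that one of the eight further carving terms had P < .05 (retention at function, P = .040).
3. **Paired comparisons.** State that none of the four dentist comparisons of carved with non-carved dentures was statistically significant (retention P = .175, stability P = .057, support P = .292, esthetics P = .824). Do not write that there was no difference.

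The cost is wording only. The figures are already in Tables 1, 6 and 7, and no new data or analysis is needed. The statement on quality of life becomes weaker than it is now.
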